6.3 Hepatotoxicity Stopping and Rechallenge Rules

Permanent Discontinuation

Subjects with abnormal hepatic laboratory values (ie, alkaline phosphatase [ALP], AST, ALT, total bilirubin [TBL]) **and/or international normalized ratio (INR)** and/or signs/symptoms of hepatitis (as described below) may meet the criteria for withholding or permanent discontinuation of Amgen IP or other protocol-required therapies as specified in the Guidance for Industry Drug-Induced Liver Injury (DILI): Premarketing Clinical Evaluation (July 2009).

6.3.1 Criteria for Withholding and/or Permanent Discontinuation of Amgen Investigational Product and Other Protocol-required Therapies Due to Potential Hepatotoxicity

The following stopping and/or withholding rules (Table 1) apply to subjects for whom another cause of their changes in liver biomarkers (TBL, INR and transaminases) has not been identified.

Important alternative causes for elevated AST/ALT and/or TBL values include, but are not limited to:

Hepatobiliary tract disease

Product: Evolocumab

- Viral hepatitis (eg, Hepatitis A/B/C/D/E, Epstein-Barr virus, cytomegalovirus, herpes simplex virus, varicella, toxoplasmosis, and Parvovirus)
- Right-sided heart failure, hypotension or any cause of hypoxia to the liver causing ischemia
- Exposure to hepatotoxic agents/drugs or hepatotoxins, including herbal and dietary supplements, plants, and mushrooms
- Heritable disorders causing impaired glucuronidation (eg, Gilbert's syndrome, Crigler-Najjar syndrome) and drugs that inhibit bilirubin glucuronidation (eg, indinavir, atazanavir)
- Alpha-one antitrypsin deficiency
- Alcoholic hepatitis

Product: Evolocumab
Protocol Number: 20130286
Date: 30 January 2017
Page 27 of 73

- Autoimmune hepatitis
- Wilson's disease and hemochromatosis
- Nonalcoholic fatty liver disease including steatohepatitis
- Nonhepatic causes (eg, rhabdomylosis, hemolysis)

Amgen IP (evolocumab/placebo) and other protocol-required therapies should be discontinued permanently and the subject should be followed according to the recommendations in Appendix A (Additional Safety Assessment Information) for possible DILI.

Rechallenge may be considered if an alternative cause for impaired liver tests (ALT, AST, ALP) and/or elevated TBL, is discovered and the laboratory abnormalities resolve to normal or baseline (Section 6.3.2).

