Table 1. Conditions for Withholding and/or Permanent Discontinuation of Amgen Investigational Product and Other Protocol-required Therapies Due to Potential Hepatotoxicity

Analyte	Temporary Withholding	Permanent Discontinuation
Total bilirubin	> 3x ULN at any time	> 2x ULN
		OR
INR		> 1.5 (for subjects not on anticoagulation therapy)
	OR	AND
AST/ALT	> 8x ULN at any time > 5x ULN but < 8x ULN for ≥ 2 weeks	In the presence of no important alternative causes for elevated AST/ALT and/or total bilirubin values
	> 5x ULN but < 8x ULN and unable to adhere to enhanced monitoring schedule	> 3x ULN (when baseline was < ULN)
	> 3x ULN with clinical signs or symptoms that are consistent with hepatitis (such as right upper quadrant pain/tenderness, fever, nausea, vomiting, jaundice)	
	OR	
ALP	> 8x ULN at any time	

ALP=alkaline phosphatase; ALT=alanine aminotransferase; AST=aspartate aminotransferase; INR=international normalized ratio; ULN=upper limit of normal.

Protocol Number: 20130286

Date: 30 January 2017

Page 28 of 73

6.3.2 Criteria for Rechallenge of Amgen Investigational Product and Other Protocol-required Therapies After Potential Hepatotoxicity

The decision to rechallenge the subject should be discussed and agreed upon unanimously by the subject, investigator, and Amgen.

If signs or symptoms recur with rechallenge, then evolocumab/placebo should be permanently discontinued. Subjects who clearly meet the criteria for permanent discontinuation (as described in Section 6.3.1) should never be rechallenged.

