For measurement of waist circumference, subjects should wear minimal clothing to ensure that the measuring tape is correctly positioned. Subjects should stand erect with the abdomen relaxed, arms at the sides, feet together and with their weight equally divided over both legs. To perform the waist measurement, the lowest rib margin is first located and marked with a pen. The iliac crest is then palpated in the midaxillary line. It is recommended to apply an elastic tape horizontally midway between the lowest rib margin and the iliac crest, and tie firmly so that it stays in position around the abdomen about the level of the umbilicus. The elastic tape thus defines the level of the waist circumference, which can then be measured by positioning the measuring tape over the elastic tape. Subjects are asked to breathe normally, and to breathe out gently at the time of the measurement to prevent them from contracting their muscles or from holding their breath. Measurements should be performed using the same procedure throughout the study. The reading is taken to the nearest centimeter or half an inch and entered in the source document.

7.4 **Laboratory Assessments**

All laboratory samples will be sent to the central laboratory, except for samples for urine pregnancy tests, which will be conducted by the local laboratory.

Concentration values are provided in mmol/L for investigator convenience. Conventional concentrations (mg/mL) will be used for the protocol, including for eligibility determination. The estimated glomerular filtration rate (eGFR) will be calculated by the central laboratory and provided to the site for eligibility determination.

The central laboratory will provide a study manual that outlines handling, labeling, and shipping procedures for all samples.

All blood samples will be obtained by venipuncture before IP administration. The date and time of sample collection will be recorded in the source documents at the site. Specific analytes for serum chemistry, urinalysis, hematology, and other labs to be conducted on blood and urine samples are shown in Table 4. Although not specifically listed, additional components, abnormal, and/or atypical cells will also be reported if present.

Product: Evolocumab Protocol Number: 20130286 Date: 30 January 2017

Page 40 of 73

Table 4. Analyte Listing

Chemistry	Urinalysis	Hematology	Other Labs
Sodium	Specific gravity	CD4	Fasting lipids
Potassium	рН	Hemoglobin	 Total cholesterol

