Subjects who receive a dose of IP at week 20 will continue in an open-label period. **They will receive their first dose of open-label IP at the week 24 visit.** Visits will **then** occur per the Schedule of Assessments (Table 3) at weeks 36 and 52. Visits during the open-label period must be completed within ± 7 days of the target visit date.

Section: 7.2.5 End of Study / Safety Follow-up

Add:

At week 52 or 30 days after the last administration of IP, whichever is later, a safety follow-up is scheduled to occur. This safety follow-up can be an in-person visit to the study center or another contact with the subject. If the end-of-study visit is < 30 days

Protocol Number: 20130286

Date: 30 January 2017 Page 15 of 20

after the last dose of IP, the subject will be contacted (eg, by phone) at 30 (± 7 days) after last IP for safety follow-up.

Section: 7.3.4 Vital Signs

Product: Evolocumab

Replace:

The position should be the same that is used throughout the study and documented on the vital sign CRF.

With:

The **same arm and same** position should be used throughout the study and documented on the vital sign CRF.

Section: 7.3.5 Safety Data Reporting

Replace:

Adverse events, serious adverse events, disease-related events, and adverse device effects observed by the investigator or reported by the subject will be collected at all study visits from the signing of the informed consent through EOS as detailed in Section 9. Only adverse events or adverse device effects possibly related to study procedures and serious adverse events are collected during screening.

With:

Adverse events, serious adverse events, disease-related events, and adverse device effects observed by the investigator or reported by the subject will be collected at all study visits from **randomization** through EOS as detailed in Section 9. Adverse events **possibly related to study procedures**, adverse device effects and serious adverse events are collected during screening.

Section: 7.4 Laboratory Assessments

Replace:

All laboratory samples will be sent to the central laboratory.

Specific analytes for serum chemistry, coagulation, urinalysis, hematology, and other labs to be conducted on blood and urine samples are shown in Table 3.

Protocol Number: 20130286

Date: 30 January 2017

Product: Evolocumab

Page 16 of 20

With:

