All laboratory samples will be sent to the central laboratory, except for samples for urine pregnancy tests, which will be conducted by the local laboratory.

Specific analytes for serum chemistry, urinalysis, hematology, and other labs to be conducted on blood and urine samples are shown in Table 4.

Section: Table 4 Analyte Listing

Delete: Coagulation (column heading)

PT/INR (table text)

Add:

Urine pregnancy test (females of childbearing potential) in Urinalysis column

Section: 7.4.2 Serum Pregnancy Test

Replace:

All females, except those who are confirmed surgically sterile or at least 2 years postmenopausal or 1 year postmenopausal if ≥ 55 years old, must have a negative serum pregnancy test at baseline, prior to administering the first dose of evolocumab/placebo. The central laboratory will provide the baseline pregnancy tests.

With:

Section: 7.4.2 Pregnancy Tests

All females, except those who are confirmed surgically sterile or at least 2 years postmenopausal or 1 year postmenopausal if ≥ 55 years old, must have a negative serum pregnancy test at screening, prior to administering the first dose of evolocumab/placebo. The central laboratory will provide the **screening** pregnancy tests.

Urine pregnancy tests will be performed on day 1 and on weeks 12, 20, 24, and 36 before IP administration and at EOS.

Section: 9.1.1 Disease-related Events

Replace:

Disease-related events and/or disease related outcomes that do not qualify as serious adverse events:

Protocol Number: 20130286 Page 17 of 20

Date: 30 January 2017

Product: Evolocumab

With:

Disease-related events and/or disease related outcomes that do not qualify as adverse events or serious adverse events:

Replace:

If the outcome of the underlying disease is worse than that which would normally be expected for the subject, or if the investigator believes there is a causal relationship between the IP/study treatment protocol-required therapies and disease worsening, this must be reported as an adverse event or serious adverse event.

With:

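### Protocol Table 1 makes INR > 1.5 a route to permanent discontinuation, but no visible current protocol text orders an INR, and the Appendix A liver-injury reporting trigger does not name it

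*Protocol*

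**What the plan says.** Table 1 in protocol Section 6.3.1 sets the permanent-discontinuation rule. Total bilirubin above 2x ULN and INR are joined by OR:

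- INR: "> 1.5 (for subjects not on anticoagulation therapy").

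Either one must then occur together (AND) with both of the following:

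- AST/ALT: "> 3x ULN (when baseline was < ULN").
- Cause: "In the presence of no important alternative causes for elevated AST/ALT and/or total bilirubin values".

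The lead-in to the table treats INR as a stopping-rule biomarker in its own right. The rules "apply to subjects for whom another cause of their changes in liver biomarkers (TBL, INR and transaminases) has not been identified". The consequence is final, because Section 6.3.2 says: "Subjects who clearly meet the criteria for permanent discontinuation (as described in Section 6.3.1) should never be rechallenged".

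On testing, Section 7.4 points to Table 4 for "Specific analytes for serum chemistry, urinalysis, hematology, and other labs to be conducted on blood and urine samples". Coagulation is not among those classes. The visible entries of Table 4 contain no PT or INR, and the visible rows of Table 3 contain no coagulation test. For potential liver injury, Appendix A asks for a repeat of transaminases, ALP and bilirubin within 24 hours, a work-up for alternative causes, and follow-up of ALT, AST and bilirubin. None of these names INR. The expedited reporting trigger in Appendix A refers to AST or ALT together with bilirubin, under the Section 6.3 criteria.

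**The concern.** A mandatory stopping rule needs its inputs. The bilirubin route can be applied from scheduled chemistry. The INR route cannot, because a site following the written plan exactly would never have an INR result to compare with 1.5.

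What is at stake is subject safety. For a subject with a moderate, unexplained transaminase rise, bilirubin at or below 2x ULN and no symptoms, an INR is the only test that separates no Table 1 action from stopping for good. Dosing is every 4 weeks, while chemistry after day 1 is scheduled only at weeks 12, 24, 36 and 52. If nobody acts between visits, doses follow at weeks 16 and 20 after a week 12 finding, and at weeks 40, 44 and 48 after a week 36 finding, before the next scheduled chemistry.

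The reporting wording raises a second, smaller issue. A case that meets the stop rule through INR is not plainly covered by the trigger meant to capture such cases.

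**Working it through.** No sample-size, power or error-rate figure is involved. The check sets the rule beside the test orders and then walks one illustrative subject through the rule.

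**1. Where INR is used.** In the current text it appears as a criterion or biomarker in Section 6.3, in the Section 6.3.1 lead-in and in Table 1.

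**2. Where INR is ordered.**

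- Routine testing (Table 3, with its test classes expanded in Table 4): not named.
- For-cause testing (Appendix A, 24-hour repeat and follow-up): not named. Appendix A also asks for retesting of unspecified liver tests, but only when bilirubin is above 2x ULN, when the bilirubin threshold has already been crossed.

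**3. Could blacked-out entries hide it?** This is unlikely. Two Table 3 rows have blank names, but they lie between the lipid and HIV rows and have no screening sample. The Amendment 1 summary of changes shows superseded Section 7.4 text that read "Specific analytes for serum chemistry, coagulation, urinalysis, hematology, and other labs", and records a deletion from Table 4: "PT/INR (table text"). The same amendment added INR to the stopping rule. The log is used here only to settle the redaction question. The point itself rests on current Table 1 against current Tables 3 and 4 and Appendix A.

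**4. Illustrative subject (assumed values).** AST/ALT 4x ULN with baseline below ULN, bilirubin 1.5x ULN, ALP 1x ULN, no symptoms, no anticoagulant, no alternative cause, INR 1.8.

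| Table 1 condition | Subject | Met? |
|---|---|---|
| Withhold: bilirubin > 3x | 1.5x | No |
| Withhold: AST/ALT > 8x | 4x | No |
| Withhold: AST/ALT 5-8x for at least 2 weeks | 4x | No |
| Withhold: AST/ALT 5-8x, enhanced monitoring not possible | 4x | No |
| Withhold: AST/ALT > 3x with hepatitis symptoms | No symptoms | No |
| Withhold: ALP > 8x | 1x | No |
| Stop, bilirubin route: > 2x | 1.5x | No |
| Stop, INR route: INR > 1.5 and AST/ALT > 3x | 1.8 and 4x | **Yes** |

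The subject meets none of the 6 withholding conditions and not the bilirubin route, but does meet the INR route. Without an INR result, Table 1 calls for no action.

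**5. Does Appendix A rescue the case?** No. Its close-observation assessments apply to subjects whose treatment has been withheld, temporarily or permanently. This subject meets no withholding condition, so the work-up starts only after an INR has been obtained and acted on.

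**6. Reporting trigger.** The trigger pairs AST or ALT with bilirubin and then cites Section 6.3. The cited criteria pair AST/ALT with bilirubin or INR, so the two do not match.

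**The case against.** The strongest reply is that this was deliberate. One amendment removed routine PT/INR and added INR to the stopping criteria, which fits a move from routine to for-cause testing. On that view, a table that gives an INR threshold already tells an investigator to consider the test when transaminases rise. That may be the intention, and it is a reasonable one. However, the for-cause order is written nowhere in the visible text. Section 7.8 permits additional safety testing on collected samples and an investigator may order an INR, but these are permissions, not orders.

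Several further points stand and limit the claim:

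- A reader might infer that the liver abnormality itself would be missed. The documents do not support that. AST, ALT and bilirubin are scheduled chemistry, the visible part of Section 7.4.1 does not list them among blinded results, Section 9.2.2.1 makes the investigator review laboratory results for clinically significant change, and treatment may be stopped on clinical judgment. SAP Section 10.6.2 also tabulates ALT or AST at or above 3x ULN.
- A reader might infer that an INR-route case would go unreported. That is not supported either. Section 9.1.4 gives drug-induced liver injury as an example of a medically important serious event, Appendix A covers other hepatotoxicity that meets serious criteria, and serious events already go to the sponsor within 24 hours. The citation of Section 6.3 can also be read as bringing INR in. The mismatch is a gap in wording.
- Appendix A introduces its assessments as a list that need not be exhaustive and requires a hepatology consult. INR's absence from its search for alternative causes is no defect, because INR measures liver function rather than cause.
- Laboratory manuals and the enhanced monitoring schedule mentioned in Table 1 are not available here and might address INR. The schedule is mentioned only for AST/ALT above 5x ULN.

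**Conclusion.** The point holds as a limited safety improvement. One of the two permanent-stop routes in Table 1 depends on a test that no visible current protocol text orders, routinely or for cause. The subjects affected have AST/ALT between 3x and 5x ULN from a baseline below ULN, bilirubin at or below 2x ULN, no symptoms, no anticoagulant and no alternative cause. Their transaminase rise would be seen. What would be missed, unless the investigator chose to order an INR, is that they meet a mandatory stop.

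This rests on the visible text and assumes that redacted entries and external manuals do not supply the order. The group is narrow, and the documents give no frequency for it, so none is estimated. No efficacy result, power or alpha is affected. The change is still worth making because the rule is mandatory, its consequence is permanent, and supplying the input is cheap.

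**What to change.** 1. In Section 6.3.1, add a footnote to the INR row of Table 1: *Obtain INR whenever AST or ALT is > 3x ULN, baseline was < ULN, and no alternative cause has been identified; a local laboratory may be used and the result recorded on the CRF.* It belongs here and not in the Appendix A close-observation list, which applies only once treatment has been withheld. Add a matching local-laboratory exception to Section 7.4, which now sends every sample except urine pregnancy tests to the central laboratory.
2. Reword the Appendix A expedited trigger to *AST or ALT with TBL and/or INR, as defined by the Section 6.3 criteria*.
3. Add INR to the Appendix A 24-hour repeat and follow-up lists, so that a subject stopped through the INR route has that value followed to resolution.

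The cost is a few lines of protocol text and a small number of unscheduled INR tests. No scheduled visit or routine sample is added. Appendix A already requires laboratory results for a potential liver-injury event to be captured on CRFs.

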4.1.2 Exclusion Criteria

- Subject taking a combination of background lipid-lowering therapy and HIV therapy known to have significant drug-drug interaction as per Table 2
- New York Heart Association III or IV heart failure, or last known left ventricular ejection fraction < 30%
- Known opportunistic infection/AIDS defining illness (including but not limited to candidiasis of bronchi, trachea, esophagus, or lungs, invasive cervical cancer, coccidioidomycosis, cryptococcosis, chronic intestinal (> 1-month duration) cryptosporidiosis, cytomegalovirus disease (particularly cytomegalovirus [CMV] retinitis), HIV-related encephalopathy, herpes simplex: chronic ulcer(s) (> 28 days duration); or bronchitis, pneumonitis, or esophagitis, histoplasmosis, chronic intestinal (> 28 days duration) isosporiasis, Kaposi's sarcoma, lymphoma, mycobacterium avium complex, tuberculosis, pneumocystis carinii pneumonia, recurrent pneumonia, progressive multifocal leukoencephalopathy, salmonella septicemia, toxoplasmosis of brain, or wasting syndrome due to HIV within 1 year prior to randomization
- 204 Myocardial infarction, unstable angina, percutaneous coronary intervention, coronary artery bypass graft or stroke within 3 months prior to randomization
- Type 1 diabetes, new-onset (hemoglobin A1c [HbA1c] ≥ 6.5% or fasting plasma glucose ≥ 126 mg/dL at screening without known diagnosis) or poorly controlled (HbA1c ≥ 10%) type 2 diabetes by central laboratory during screening
- 206 Uncontrolled hypertension defined as sitting systolic blood pressure > 180 mmHg or diastolic blood pressure > 110 mmHg during screening
- Subject has taken a cholesterylester transfer protein inhibitor in the last 12 months prior to randomization
- 208 Moderate to severe renal dysfunction, defined as an estimated glomerular filtration rate < 30 mL/min/1.73 m² during screening

Date: 30 January 2017 Page 21 of 73

209 Persistent active liver disease or hepatic dysfunction defined as Child-Pugh score of C. Stable (in the opinion of the primary investigator and with aspartate aminotransferase [AST] and alanine aminotransferase [ALT] < 5 times ULN and not expected to require new treatment[s] during study) chronic hepatitis C of at least 1 year duration prior to randomization is allowed

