Appendix A. Additional Safety Assessment Information

Adverse Event Grading Scale

Refer to the NCI Common Terminology Criteria for Adverse Events (CTCAE) Version 4.0. The CTCAE is available at the following link:

http://ctep.cancer.gov/protocolDevelopment/electronic applications/ctc.htm

Drug-induced Liver Injury Reporting & Additional Assessments Reporting

To facilitate appropriate monitoring for signals of DILI, cases of concurrent AST or ALT and TBL according to the criteria specified in Section 6.3 require the following:

- The event is to be reported to Amgen as a serious adverse event within 24 hours of discovery or notification of the event (ie, before additional etiologic investigations have been concluded)
- The appropriate CRF (eg, Event CRF) that captures information necessary to facilitate the evaluation of treatment-emergent liver abnormalities is to be completed and sent to the Amgen.

Other events of hepatotoxicity and potential DILI are to be reported as serious adverse events if they meet the criteria for a serious adverse event defined in Section 9.2.2.2.

Additional Clinical Assessments and Observation

All subjects in whom IP or protocol-required therapies is/are withheld (either permanently or conditionally) due to potential DILI as specified in Sections 6.3.1 and 6.3.2 or are to undergo a period of "close observation" until abnormalities return to normal or to the subject's baseline levels. Assessments that are to be performed during this period include:

- AST, ALT, ALP, and bilirubin (total and direct) is to be repeated within 24 hours
- In cases of TBL > 2x ULN, retesting of liver tests, and bilirubin (total and direct) is to be performed every 24 hours until laboratory abnormalities improve

Product: Evolocumab
Protocol Number: 20130286

Date: 30 January 2017 Page 68 of 73

Testing frequency of the above laboratory tests may decrease if the abnormalities stabilize or the IP or protocol-required therapies has/have been discontinued AND the subject is asymptomatic.

- Initiate investigation of alternative causes for elevated AST or ALT and/or elevated TBL:
 - Obtain complete blood count with differential to assess for eosinophilia
 - Obtain serum total immunoglobulin IgG, Anti-nuclear antibody (ANA), Anti Smooth Muscle Antibody, and Liver Kidney Microsomal antibody 1 (LKM1) to assess for autoimmune hepatitis
 - Obtain serum acetaminophen (paracetamol) levels
 - Obtain a more detailed history of:

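### Table 1's permanent-stop rule gives no AST/ALT limit for a baseline at or above ULN, so a narrow band of unexplained, symptom-free combined liver rises requires no action

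*Protocol*

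**What the plan says.** **Permanent stop.** The right-hand column of Table 1 (Protocol 6.3.1) combines bilirubin > 2x ULN or INR > 1.5 (if not anticoagulated) with an AST/ALT condition, "> 3x ULN (when baseline was < ULN", and requires that no important other cause is present. This is its only AST/ALT limit. The amendment's summary of changes shows the same cell.

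**Temporary withholding.** The other column applies at any baseline: bilirubin > 3x ULN; AST/ALT > 8x ULN; AST/ALT "> 5x ULN but < 8x ULN for ≥ 2 weeks", or in that range when enhanced monitoring cannot be kept up; AST/ALT > 3x ULN with signs or symptoms of hepatitis, jaundice included; or ALP > 8x ULN. All of Table 1 is limited to subjects with no other identified cause for the change.

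**Who is admitted.** Criterion 209 (4.1.2) allows stable chronic hepatitis C with AST and "alanine aminotransferase [ALT] < 5 times ULN and not expected to require new treatment[s] during study". Section 4.1.2 sets no other AST/ALT limit.

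**Rechallenge.** Section 6.3.1: "Rechallenge may be considered if an alternative cause for impaired liver tests (ALT, AST, ALP) and/or elevated TBL, is discovered", and the values must also have returned to normal or baseline. Section 6.3.2 adds unanimous agreement of subject, investigator and sponsor, and two further rules: "Subjects who clearly meet the criteria for permanent discontinuation (as described in Section 6.3.1) should never be rechallenged" and "If signs or symptoms recur with rechallenge, then evolocumab/placebo should be permanently discontinued".

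**Follow-up.** Appendix A's close observation covers subjects whose product is "withheld (either permanently or conditionally) due to potential DILI as specified in Sections 6.3.1 and 6.3.2". Its automatic 24-hour report is for "cases of concurrent AST or ALT and TBL according to the criteria specified in Section 6.3 require the following".

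**The concern.** The protocol plans to include people with raised transaminases and stratifies randomization by hepatitis C status. Yet the strongest liver rule is written only for a baseline below ULN. A subject whose AST and ALT both start at or above ULN cannot meet the initial permanent-stop criterion, and so the rechallenge ban tied to it never attaches.

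What is at stake is an unexplained combined rise in transaminases and bilirubin. From a baseline just under ULN it means a mandatory permanent stop. From a baseline just over ULN, the same later values can meet neither column. Product then need not be stopped or withheld, and the repeat tests and close observation in Appendix A are not triggered. By Table 3, chemistry is next scheduled 12 or 16 weeks later. After the visit-day dose, the subject would be due doses at weeks 16 and 20, at 28 and 32, or at 40, 44 and 48 before that draw, unless the investigator intervenes.

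**Working it through.** This is a decision rule, so there is no plan figure to reproduce. The check applies both columns of Table 1 to given values.

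**Inputs.** Table 1 limits and criterion 209, as set out above. Let *b* be the baseline, in multiples of ULN, of the analyte that rises, with both AST and ALT at or above ULN at baseline. One assumption is added: a meaningful rise is one above 3*b*. No document gives a multiple for raised baselines. The value 3 makes the limit continuous with the existing one, since 3*b* = 3x ULN at *b* = 1.

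**1. Permanent column.** It needs an analyte with baseline < ULN. If both are at or above ULN, no later AST, ALT, bilirubin or INR value satisfies it. If only one was raised, the other can still trigger it. With baseline AST 0.9x and ALT 1.2x, and later ALT 4.5x and bilirubin 2.5x, the rule is met if AST reaches 3.2x and not met if AST is 2.5x.

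**2. Worked example.** Baseline AST 1.1x, ALT 1.2x. Later AST 3.0x, ALT 4.5x, bilirubin 2.5x, ALP < 2x ULN, no signs or symptoms, no cause found.

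- Own-baseline ratios: ALT 4.5/1.2 = 3.75; AST 3.0/1.1 = 2.73.
- Permanent column: not met, because neither baseline was < ULN.
- Withholding column: bilirubin is not > 3x, AST/ALT are not > 5x, there are no symptoms and ALP is not > 8x. Not met.
- Same later values from baselines of 0.9x: ALT 4.5x > 3x with bilirubin 2.5x > 2x, so permanent stop.

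**3. Extent of the band** (bilirubin > 2 to 3x ULN, no signs or symptoms, ALP no higher than 8x ULN). The upper edge is 5x ULN for a rise of any duration. It is 8x ULN for a rise lasting under 2 weeks with enhanced monitoring followed. The edges in *b* are 5/3 = 1.67 and 8/3 = 2.67.

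| *b* | 3*b* | Band up to 5x ULN (width 5 - 3*b*) | Short-lived band up to 8x ULN |
|---|---|---|---|
| 1.0 | 3.0 | 3.0-5.0 (2.0) | 5-8 |
| 1.2 | 3.6 | 3.6-5.0 (1.4) | 5-8 |
| 1.5 | 4.5 | 4.5-5.0 (0.5) | 5-8 |
| 1.67 | 5.0 | closed | 5-8 |
| 2.0 | 6.0 | closed | 6-8 |
| 2.5 | 7.5 | closed | 7.5-8 |
| 2.67 and above | 8.0 or more | closed | closed |

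**4. INR branch.** INR > 1.5 with bilirubin at or below 3x ULN opens the same band. It matters only if INR is measured, and Table 4 does not list it.

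**5. Above the withholding limits.** Product is withheld at any baseline. Rechallenge then needs a discovered alternative cause, resolution and unanimous agreement. If no cause is found, withholding is in effect permanent. Recurrence on rechallenge is a permanent stop at any baseline.

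**The case against.** The strongest reply is that the baseline qualifier looks deliberate. The superseded criterion in the amendment's summary also required a rise from below ULN, and the section was rewritten to current sponsor guidelines with the qualifier kept. A fixed 3x ULN limit would be wrong for someone starting at 4x ULN. Withholding limits and judgment cover the rest: laboratory changes are reviewed against baseline (9.2.2.1), treatment can end for a safety concern or by physician decision (8.3.1), and drug-induced liver injury is a named example of a medically important serious event (9.1.4). This stands as a reason not to apply 3x ULN to everyone. It does not explain why no baseline-relative limit is given. Judgment applies equally to normal-baseline subjects, for whom a mandatory rule was still written.

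Three stronger readings are tempting, and the documents do not support them.

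- *Hepatitis C subjects up to 5x ULN have no liver stopping protection.* Withholding covers larger or symptomatic rises and is effectively permanent without a cause. Viral hepatitis and bilirubin-raising drugs such as atazanavir are listed alternative causes, so many such cases fall outside Table 1 altogether. A new, unexplained rise in a stable hepatitis C subject stays within it.
- *The SAP contradicts the protocol.* SAP 10.6.2 tabulates ALT or AST at least 3x ULN with bilirubin at least 2x and ALP < 2x ULN, with no baseline condition. That is a descriptive summary, not a stopping rule.
- *Many subjects are exposed.* The documents give no hepatitis C share and no baseline AST/ALT distribution.

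It is also fair to say that the 3x multiple is a preference. Section 6.3 cites an external liver-injury guidance whose content is not used here.

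**Conclusion.** The omission is real on the text, and it is narrow. For subjects with both AST and ALT at or above ULN at baseline, an unexplained, symptom-free combined rise below the withholding limits requires no stop, no withholding and no Appendix A close observation. From a baseline of 0.9x ULN the same values can require a permanent stop. On the assumed yardstick the gap lies between 3x baseline and 5x ULN for baselines from 1 to < 1.67x ULN. It extends to short-lived values of 5-8x ULN for baselines < 2.67x ULN.

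Without the yardstick, values above both 3x ULN and baseline, up to 5x ULN, meet no limit at any admitted raised baseline. At high baselines these are small relative rises (4.0x to 5.0x is a factor of 1.25), where leaving the decision to judgment is reasonable.

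Frequency cannot be derived and is probably low, since several conditions must coincide and be seen at a chemistry draw. This is a cheap patient-safety improvement with no bearing on the efficacy analysis.

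**What to change.** By amendment, change only the AST/ALT limit in the permanent column of Table 1 to: *> 3x ULN if that analyte's baseline was < ULN; > 3x own baseline if that analyte's baseline was >= ULN*. Keep the bilirubin/INR condition, the requirement that no alternative cause is present, and every withholding limit. The medical team should confirm the multiple.

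In the worked example ALT 4.5x then exceeds 3 x 1.2 = 3.6x ULN and a permanent stop follows. At a baseline of 4.9x the stop needs > 3 x 4.9 = 14.7x ULN, so a small rise over a high baseline does not force one; withholding at > 8x ULN acts first. The rechallenge ban and the Appendix A steps then apply without further edits.

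The cost is one table cell and probably a few additional permanent discontinuations. AST, ALT and total bilirubin are already in Table 4. Rises of less than 3x baseline remain a matter of judgment: a subject going from ALT 1.6x to 4.7x ULN (ratio 2.94) with bilirubin 2.5x ULN would still meet no limit.
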